6.1.1 Study Intervention Description

Medications:

Investigational Agent XRBUP (CAM 2038, Brixadi) is a subcutaneous (SC) extended-release formulation of buprenorphine that has been developed by Camurus AB (Sweden) and licensed in the US by Braeburn Pharmaceuticals. Differences between Brixadi and the alternative FDA-approved injectable XRBUP Sublocade is that it is available in a range of weekly and monthly doses (8,16,24 and 32 mg weekly and 64mg and 96mg and 128mg monthly), unlike Sublocade, it does not require abdominal SC injection and is expected to be less expensive than Sublocade (Lofwall et al 2018). Weekly Brixadi doses for the study will use a combination of 8mg, 16mg, and 24mg doses not exceeding 32mg. Monthly Brixadi doses will be either 64mg, 96mg, or 128mg.

Brixadi was approved under brand name Buvidal for OUD by the European Medicines Agency and On May 23, 2023, The U.S. Food and Drug Administration granted approval of Brixadi to Braeburn Inc. . Braeburn, the US licensee of Brixadi has agreed to provide the study medication at no cost (See Letter of support).

6.2 XRNTX (Vivitrol):

is a monthly extended-release intramuscular injection of 380 mg of naltrexone manufactured by Alkermes Inc, that has been approved by the FDA for OUD since 2010 (Lee et al 2017) XRNTX maintains therapeutic levels of naltrexone and its active metabolites for approximately 4 weeks after each injection. We plan to purchase Vivitrol required for the proposal.

Preparation/Handling/Storage/Accountability

6.2.1 Acquisition and accountability

Investigational agent (Brixadi, XRBUP) is manufactured and supplied by Braeburn. It will be stored and dispensed by the Research Pharmacy at the Hospital of the University of Pennsylvania consistent with regulations governing a DEA Schedule III medication.

Upon receipt of the of the study treatment supplies, an inventory will be performed, and a drug receipt log filled out and signed by the person accepting the shipment. It is important that the designated study staff counts and verifies that the shipment contains all the items noted in the shipment inventory. Any damaged or unusable study drug in a given shipment (active drug or comparator) will be documented in the study files.

6.2.2 Formulation, Appearance, Packaging, and Labeling

Please refer to the Vivitrol and Brixadi product package insert

6.2.3 Product Storage and Stability

In compliance with Office of Clinical Research guidelines for outpatient clinical trials using industry drug, study medications will be received, packaged and stored at PENN's Investigational Drug Service (IDS). Upon receipt of the study medication, an inventory will be performed and a drug receipt log filled out and signed by the person accepting the shipment. IDS staff will verify that the shipment contains all the items noted in the shipment inventory. Any damaged or unusable study medication in a given shipment will be documented in the study files. IDS will oversee assigning and labeling of all study medication. Study medications will be kept separate from all other samples, and drugs and clearly labelled as investigational product. XRNTX and XRBUP will be stored at the appropriate temperatures as determined by the manufacturer. Both cold and room temperature storage (if applicable) will be kept secured locked and accessible only to those working on the study. Accountability logs (subject level & study-wide) will be kept ensuring thorough documentation of shipping, handling, storage, preparation, and dispensing of study medication.

6.2.4 Preparation

Study medication will be prepared at PENN's Investigational Drug Service (IDS) and administered by clinical research staff (RNs) on-site at the Addiction Treatment Center ([name]) who have received documented and thorough training on the knowledge of the study medications, purpose, side effects, and precautions. Inventory, dispensing, and logging of study medications

will be conducted on a trial-level and individual subject basis. As per OCR guidelines, study medications are *not* re-packaged prior to administration. A separate study medication destruction log will be kept if unused medication is not returned to the manufacturer as per manufacturer's specifications for the trial. All procedures, instructions and documentation requirements as defined by the Office of Clinical Research for management of investigation sites using FDA regulated drugs using IDS will be followed.

6.3 Measures to Minimize Bias: Randomization and Blinding

Urn Randomization. We plan to use urn randomization to stratify subjects across the two treatment conditions. We will stratify subjects on sex on the day of randomization.

An off-site statistician will work with clinical research staff in setting up the urn randomization sequences and will ensure that the codes linking subject's ID numbers to treatments are secure. Randomization uses an electronic emergency-unmasking database in Microsoft Access accessible to the off-site statistician 24 hours a day.. Randomization tables are secured within Microsoft Access and are managed by an off-site statistician and data management study personnel, who do not work directly with study participants. The system only provides access for one subject at a time and all transactions are recorded. If a subject is prematurely discontinued from the trial, all attempts will be made to not break the blind. If an emergency necessitates that the blind be broken, only the off-site statistician will have access to the blind to do so. They will be given the name of the staff members who have authority to request that the blind be broken. The off-site statistician can be reached 24 hours a day and can access a subject's code rapidly.

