9 STATISTICAL CONSIDERATIONS

9.1 Statistical Hypotheses

Overview of primary hypotheses: Our primary response will be a binary indicator of treatment failure on the XRNTX or XRBUP regimen, defined as ≥ 2 weekly UDS positive for opioids, or self-report of ≥ 2 periods of three or more days of opioid use, or refusing XRNTX or XRBUP, or dropping out of study entirely. In hypotheses H1a and H1b, we are examining the effects of small, pre-specified, sets of measures, so our analyses will focus on model fit and prediction, and not on model selection. In hypothesis H1c, we search for best sets of predictors among demographic and clinical-behavioral variables, and over sets of brain/neural measures, so our focus is on model selection and on avoiding overfitting to the available data.

R61 Phase:

Hypothesis H1 (fMRI): For each of the cue reactivity (H1a), response inhibition (H1b), and connectivity (H1c) brain measured, we have a small number of neural responses associated with one or two regions of interest. These variables are continuously distributed, so we will test Hypotheses 1a, 1b and 1c using a repeated measures analysis of variance (rm-anova). The models will include a within-subject factor for Session (PRE vs ON) and a between-subject factor Group (XRNTX vs XRBUP), and their interaction. To accommodate the anticipated non-normal distributions of the response, we will use a generalized estimating equation (GEE) approach, using robust standard errors, using a compound symmetry working correlation structure for the within-subject correlations between the PRE and ON fMRI scans (Diggle PJ et al 2002). We will perform the rm-anova separately for each ROI (mPFC and VS for H1a, IFC for H1b, and VS-rtIFG and VS-mPFC for H1c). The hypotheses will be addressed by the Session by Group interaction, and we will obtain estimates and standard errors of the PRE vs ON change within each of the two groups, along with the size, standard error and significance of the differences between these estimates.

Sample size considerations for sample: The sample size is adequate for application of the GEE methods to obtain robust standard error (Lipsitz et al 1994). For a test of the PRE vs ON effect, our sample yields 80% power for a one-sided test that the ON levels will be Cohen's $d=0.4$ lower than the PRE levels, consistent with a decrease of Cohen's $d=0.5$ observed in our preliminary data and a decrease of Cohen's $d=0.3$ in the Suboxone sample.

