Milestone for transition from Phase 1 to Phase 2: Using the models described above, we will obtain (model-based) estimates of the Session (PRE vs ON) by Group (XRNTX vs XRBUP) effects for the five hypotheses described above. If these estimates show at least small effects (Cohen's $d \geq 0.2$) in at least two of the three domains, then we will continue to the R33 phase.

Primary Analyses for Phase 2: Session by Group interaction effects on neural response: First, we will formally test the interaction effects explored in the R61 phase. We will rerun the analyses described for H1a, H1b and H1c in the R61 phase, for the full sample of $n=140$ obtained through the R61 and R33 phases. The models will be exactly as described in the R61 phase.

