Effects of neural response on relapse vulnerability: Our primary outcome combines adherence to treatment and frequency of illicit opioid use during treatment. The primary outcome is a binary indicator of treatment success: if a patient provides ≥ 2 weekly UDS positive for opioids, or self-report of \geq two or more periods of ≥ 3 days of opioid use, or refuses XRNTX or XRBUP, or drops out of treatment entirely, then they will be classified as a treatment failure; otherwise they will be classified as a treatment success. We will calculate the PRE-ON change in %-signal-change for each of the regions and neural responses described in the R61 phase. We will use logistic regression models to predict the log-odds of treatment success (Aitkin et al 2009). The predictors in the model will be a binary factor for Group (XRNTX vs. XRBUP), and the neural change scores. We anticipate that there will be some greater PRE to ON changes in the XRNTX group than in the XRBUP group, so there will be some confounding between the effects of change score and the effects of Group on the rates of positive UDS. Thus, we will include Group first in our model, so evaluating the Group effect separate from the change-score effects, and then include the change scores in a model including Group, so evaluating the additional effect of change-scores in addition to the existing effects of Group. To assess whether the effects of the change scores differ between the XRNTX and XRBUP groups, we will also test for interaction effects between Group and each of the change-scores, by adding the interaction terms to the model that includes the group and neural change score main effects. We will check the assumptions underlying the logistic regression models (e.g. linearity of covariates effects on log-odds, outliers, influential observations) using standardized residuals, influence diagnostics, and graphical displays.

Sample size considerations for the sample: Analyses of Session by Group effects on neural response: For a one-sided test that the PRE vs ON effect is larger in the XRNTX group than in the XRBUP group, our sample of 70 per group yields 81% power for an effect of $d=0.42$ or greater. This effect is similar to the effects observed in the preliminary data. On the basis of the preliminary data we anticipate Group by Session effects of approximately $d=0.38$ in the VS and $d=0.42$ in the mOFC.

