Predictive modeling: The models for relapse/treatment-success addressed the effects of neural responses, in isolation from demographic and clinical measures. In further analyses, we will examine their effects in combination with demographic and non-imaging clinical predictors. As we can expect overlap between the effects of these sets of variables, we compare the effects of these domains on prediction of treatment success. Thus, we will compare models using various sets of predictors on the basis of AUC comparisons, rather than on goodness of fit (Sullivan Pepe 2003). In our model search, we will compare models containing interactions between Group and the various predictors, with the constraint that an interaction is included only in models where the corresponding main effects are also included. First, we will find the best fitting demographic model, searching over a set including age, race, gender, and educational status. Next, with the predictors from the best demographic model included, we will search over the clinical predictors (depression and anxiety scores, measures of withdrawal and craving, and the ASI composite scores) to find the set that most improves the predictive utility of the best demographic model. Third, with the predictors from the best demographic/clinical model included, we will search over the measures of neural change to find the set that most improves the fit of the best demographic/clinical model. We will then perform goodness of fit and ROC comparisons between the best demographic, demographic/clinical, and demographic/clinical/brain models. This process involves three searches over various sets of variables, and unconstrained searches are likely to yield complex models involving many predictors, resulting in a prediction rule that performs poorly in new samples. To avoid this, we will use a lasso approach to fitting the logistic regression models for this hypothesis. The usual algorithms for logistic regression estimate the model parameters by minimizing a measure of lack of fit of the model to the data, but do not penalize models for complexity. The lasso approach selects a best fitting model subject to the constraint that the sum of the magnitudes of the regression coefficients in the model is less than a small positive threshold value. The threshold is chosen adaptively from the data, by minimizing an estimate of the prediction error for the model, using ten-fold cross validation. Then, a best fitting model is chosen with the estimated threshold used in the penalty. The best fitting model is usually one in which a number of the coefficients are set to zero, i.e. a number of predictors are dropped from the model.

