9.4 Statistical Analyses

9.4.1 General Approach

Data Management. Data will be gathered using Penn's REDcap data collection system, a direct-entry data system where subjects can directly enter responses. REDcap is HIPAA compliant and data is secured on Penn Medicine's data management unit (DMU) network. Interview data and self-report data are entered directly into REDcap at the research sites, by research technicians and study subjects respectively. Field validation (eg, no out of range or otherwise invalid responses will be accepted) and form validation (e.g. logically impossible responses to different questions will not be accepted) are built into this entry process. Data are transmitted (128-bit encrypted form) over the internet to the DMU servers. After online reviews, the data are archived on the servers. Certain DMU staff members have permission to modify the archived data. Audit logs record any modification to the original entry. Password protection allows members of the research team appropriate levels of data access. At time of data collection clinical research staff will review data collected for completeness (field and form validation). Weekly routine data inspections will be performed by clinical research staff to ensure data integrity. Subject brain scan data are extracted via CAMRIS web-servers and are archived to lab-specific, encrypted servers for standard cleaning and analysis.

Data Analyses. [name], the CSA Statistician, and his staff will perform the data analyses. Prior to analyses, standard data screening/cleaning procedures will be applied ⁵³. These procedures will screen the data for data-entry errors, check for outliers, assess the extent and pattern of missing data, and check that appropriate assumptions of normality are met whenever necessary. Due to sample size, it is unlikely that the randomization will result in significant imbalance of the distributions of demographic or other variables across treatment groups. Additional covariates will be considered for inclusion in the analyses, to improve the precision of estimation for the treatment effects. Covariates describing levels of cocaine use prior to the study may be included. Assumptions underlying the application of statistical methods will be examined, through use of standardized residuals, influence diagnostics, and graphical displays.

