Missing Data and Nonadherence: For the longitudinal analyses described above, premature discontinuation from treatment and occasional missing daily use indicators will lead to incomplete data. The mixed effects models described above can make use of all available data provided by subjects, but the inferences drawn from them will be unaffected by the missing data only if the missing data can be regarded as ignorable, in the sense of Laird ⁵⁵. To assess the sensitivity of our analyses to this assumption, we will use shared parameter models, which allow for correlated random effects underlying the cocaine use measurements and the pattern of dropout ⁵⁶. We will also use selection models to examine the effects of missing data ^{57,58}. We will explicitly model the probability of premature discontinuation at a time point as a function of baseline characteristics and responses at previous time points, using a logistic regression model, and incorporate the predicted probabilities into a weighted analysis of the main hypotheses. We will do analyses in a range of assumptions and assess the sensitivity of results to them ⁵⁸. We will use urine drug screens, record of clinic visits and receipt of injectable medications as measures of compliance with assigned medication regime. We will use the methods of Nagelkerke et al ⁵⁹ and Small et al ⁶⁰, to obtain estimates of the intervention effect in a population compliant with treatment i.e. the Complier Average Causal Effect (CACE).

Safety: The adverse event responses will be analyzed as a measure of safety. Total number of adverse events, adverse events leading to discontinuation (in the judgment of the study physician), % of patients reporting at least one adverse event, clinical lab assessments, vital signs and

evidence of clinical worsening (by urine drug screen results and TLFB results) will be considered in assessment of safety. In a manner parallel to the analysis for therapeutic response, medication group, gender, age and other clinical variables will be entered into a generalized linear mixed effects model to predict adverse events.

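### Randomisation is stratified on sex, but the Session-by-Group ROI models have no prespecified sex-by-Session term, so a valid test is slightly conservative

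*Combined protocol and SAP*

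**What the plan says.** Section 6.3 (Randomization and Blinding) uses urn randomisation with one named factor: "We will stratify subjects on sex on the day of randomization".

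Section 9.1 (R61 Phase) gives the model for hypotheses H1a to H1c: "The models will include a within-subject factor for Session (PRE vs ON) and a between-subject factor Group (XRNTX vs XRBUP), and their interaction". It is fitted by GEE, "using robust standard errors, using a compound symmetry working correlation structure for the within-subject correlations between the PRE and ON fMRI scans", separately for each ROI. For the confirmatory phase, the same section says: "The models will be exactly as described in the R61 phase". No sex term appears in either place, and the restated hypotheses in section 9.4.1 add none.

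The logistic model of treatment success in section 9.1 is also listed without sex: "The predictors in the model will be a binary factor for Group (XRNTX vs. XRBUP), and the neural change scores". Group-by-change-score interactions are added afterwards.

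Three other places bear on the point:
- Section 9.4.1 (Data Analyses): "Additional covariates will be considered for inclusion in the analyses, to improve the precision of estimation for the treatment effects". The only example it gives is prior cocaine use, which is optional.
- Section 9.1 (Predictive modeling): gender is a candidate in the demographic step, "searching over a set including age, race, gender, and educational status".
- Section 9.4.1 (Safety): "medication group, gender, age and other clinical variables will be entered into a generalized linear mixed effects model to predict adverse events".

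**The concern.** When allocation is balanced on a factor that predicts the outcome, the treatment difference varies less from trial to trial than it would under simple randomisation. A model without that factor does not see this. It leaves the factor's variance in the residual and reports a standard error that is somewhat too large. The robust standard error does not help: it protects against a wrong within-subject correlation, but carries no information about how participants were allocated.

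What is at stake is some power in the Session-by-Group tests, and a choice left open in an open-label trial. If sex is not fixed in advance, whether to adjust for it can be decided after the data are seen.

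**Working it through.** **Inputs.** From section 9.1 (sample size paragraph for Phase 2): 70 per group, d=0.42, one-sided test, stated power 81%. The alpha for this test is not stated. I take one-sided 0.05, because section 9.1 uses 0.05 for its logistic power and because this choice reproduces the stated figure. The share R² of variance in PRE-to-ON change explained by sex is **not in the documents**; 0 to 0.10 is my assumed range.

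**Step 1: reproduce the plan's power.** For a two-group comparison of change scores:
- δ = d·√(n/2) = 0.42·√35 = 2.485
- power = Φ(δ − 1.645) = Φ(0.840) = 80.0%

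This is close to the stated 81%. One-sided 0.025 gives 70.0%. Section 9.2 quotes the same 81% for 80 per group, where the formula gives 84.4%. I therefore work with 70.

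**Step 2: effect of leaving sex out.** Let k = √(1 − R²), with sex balanced between arms in the analysed sample. The unadjusted model reports SE, while the true sampling SD is k·SE. Then:
- overstatement of the SE = 1/k − 1
- actual one-sided alpha, unadjusted = 1 − Φ(1.645/k)
- power, unadjusted = Φ((δ − 1.645)/k)
- power, adjusted = Φ(δ/k − 1.645)

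| R² (assumed) | SE too large by | Actual alpha, unadjusted | Power, unadjusted | Power, adjusted | Gain (points) |
|---|---|---|---|---|---|
| 0 | 0% | 0.0500 | 80.0% | 80.0% | 0 |
| 0.02 | 1.0% | 0.0483 | 80.2% | 80.7% | 0.5 |
| 0.05 | 2.6% | 0.0457 | 80.6% | 81.7% | 1.1 |
| 0.10 | 5.4% | 0.0415 | 81.2% | 83.5% | 2.3 |

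**Step 3: simulation check.** Settings: 140 participants, urn within sex, 40% female (assumed), robust SE, 4,000 runs per setting. At R²=0.10 the mean unadjusted SE was 0.169 and the mean adjusted SE 0.160, a ratio of about 1.05, as in the table. The empirical SD of the unadjusted estimate was about 0.164, so against its own sampling SD the unadjusted SE was too large by about 3% (0.169/0.164 = 1.03). This is less than 5.4% because an urn balances only approximately. Power was 80.6% unadjusted and 83.2% adjusted. At R² of 0.02 and 0.05 the differences are too small to separate clearly from simulation error.

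**Step 4: which term is needed.** The target is a within-person change, so a constant sex difference in signal level cancels. One simulated GEE data set, with sex balanced across arms, shows this for the Session-by-Group term:

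| Model | Estimate | Robust SE |
|---|---|---|
| Session × Group | −0.1732 | 0.1662 |
| plus sex | −0.1732 | 0.1662 |
| plus sex and sex × Session | −0.1732 | 0.1644 |

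Only the sex-by-Session term changes the standard error.

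**Step 5: the logistic model.** The formula in Step 2 does not carry over. In a simulation with 140 participants, sex balanced, Group odds ratio 1.25 and neural odds ratio 1.75 (both from section 9.1), and 40% female with an event rate of about 45–50% (both assumed), adding sex **raised** the mean SE of the Group log odds ratio. It went from 0.357 to 0.360 for a sex odds ratio of 1.5, from 0.356 to 0.363 for 2, and from 0.355 to 0.369 for 3. The SE of the neural term also rose, from 0.194 to 0.198 at a sex odds ratio of 2.

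**The case against.** The strongest reply is that nothing is invalid. The actual alpha never exceeds 0.05 in Step 2, the gain is at most 2.3 points over the assumed range, and it is zero if sex does not predict change. Balance in the analysed sample is also only approximate. The second scan is at day 55, section 9.1 anticipates 25% dropout (in its secondary substance-use analyses), and section 5.3 budgets 10% extra scanner time for data loss. All of this stands, and it is why the point is minor.

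A second reply is that section 9.4.1 already provides for covariates that improve precision. It does so only as an option, without naming sex, beside Phase 2 models that are to be rerun unchanged. It permits adjustment but does not prespecify it.

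Two stronger readings are tempting, and the documents do not support them:
- A reader might infer that the logistic models also give up precision by omitting sex. Step 5 shows the reverse for the standard error. Adjustment there changes the Group odds ratio from marginal to conditional, and any power gain would have to come from the larger conditional effect. The neural change scores tested in that model are not randomised, so stratified allocation is no argument about their standard errors.
- A reader might infer that the plan contradicts itself because its safety model includes gender. That model serves another purpose and also takes in age and other clinical variables. Its text says it runs parallel to the therapeutic response analysis, which could even be read as intending gender there too. This is an ambiguity to clear up, not a contradiction.

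**Conclusion.** The point holds for the Session-by-Group ROI models, as a small loss of efficiency and an open analyst choice. Sex is the factor the trial randomises on, and no prespecified term in the primary interaction model uses it. Over an assumed R² of 0 to 0.10, with sex balanced among scanned participants, the unadjusted test has actual one-sided alpha between 0.0500 and 0.0415, and adjustment gains 0 to 2.3 power points at 70 per group and d=0.42. With the approximate balance an urn gives, the conservatism is somewhat smaller.

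That standard errors which ignore stratification undermine the inference would be the wrong conclusion: the error is on the safe side. For the logistic models there is a separate and weaker case. Sex could confound the association between neural change and treatment success, and naming it would fix which conditional Group odds ratio is being estimated.

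**What to change.** In section 9.1, state that each ROI model includes sex and sex-by-Session as fixed, prespecified terms in both phases. Both are needed: sex alone leaves the Session-by-Group term as it was. An equivalent form is to analyse the change score with sex as a covariate.

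If wanted, also prespecify sex in the logistic models of treatment success, giving confounding and the conditional odds ratio as the reason. In section 9.4.1, separate these fixed terms from the optional covariates, and say whether the reference to a parallel therapeutic response analysis is meant to bring gender into that analysis.

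The cost is one or two sentences and one or two degrees of freedom per ROI model. Sex is already recorded for randomisation, so no new data are needed.
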